2.2.2 Eligibility criteria

Inclusion criteria will be: 1) ≥ 55 years of age, 2) normal or corrected-to-normal vision with glasses or contact lenses, 3) no locomotion impairments, 4) a maximal body weight of 135 kg, and 5) a maximal body height of 200 cm. Limitations regarding body weight and body length are due to the design of the Lokomat gait exoskeleton.

Participants will be excluded if they: 1) have skin lesions that cannot be protected appropriately, 2) have had significant lower extremity injuries during the last two years that might affect their gait, and 3) have any type of vestibular/visual deficiency.

2.3 Instrumentation

2.3.1 Virtual reality

The virtual reality will be provided by a HMD VR system 'Oculus Rift' (Oculus rift, LLC, US) and will assure an immersive virtual environment. The experimental group will walk in a more interactive VE such as a park or city streets, while the VE of the control group will represent an endless hallway where subjects will have to walk through.

2.3.2 Robot-assisted gait training

The Lokomat (version LokomatPro V6) gait exoskeleton (Hocoma AG, Volketswil, Switzerland) comprises two actuated leg orthoses and is used in conjunction with a body-weight support and treadmill. It has four degrees of freedom, allowing to control the movements of the hip and knees in the sagittal plane. Foot lifters can be used to assist the dorsiflexion, necessary for foot clearance during the swing phase. Furthermore, the Lokomat has force and position sensors in each hip and knee joint to measure the interaction torques between orthosis and participant and the range of motion, respectively.

2.4 Procedure

Participants will be tested during one VR enhanced RAGT session at the rehabilitation center TrainM (Antwerp).

Prior to the start of the experiment, surface electrodes will be placed bilateral on the Mm. rectus femoris and Mm. biceps femoris to measure muscle activity. Electrode placement will follow as closely as possible the guidelines of SENIAM [16]. The skin underlying the electrode will be shaved and cleaned to improve electrode–skin contact and reduce impedance.

At the start of the session, participants will be habituated to walking in the Lokomat without the virtual reality. During this habituation trial, the appropriate settings to walk comfortable in the exoskeleton will be determined. To make sure all participants walk comfortable in the Lokomat, subjects will be provided with a body weight support (BWS) of 30%. Guidance force (GF) will be set on 80% for all participants. With lower levels of GF, the biofeedback values will show smaller changes and can become negligible. Lastly, the walking speed (WS) will be set at 2.8 km/h for all participants (setting Lokomat: see Appendix). Preparing and installing the participant and determining the appropriate Lokomat settings will take no longer than 20 minutes. When the Lokomat settings are defined, the Lokomat will be stopped for a moment so that the virtual reality can be added. Participants will put on the HMD and will start walking again for one minute while watching the virtual environment scene expanding at a speed matching their walking speed to get used to the VR. After the habituation trial, participants will walk in the Lokomat with the three different OF speeds [10, 15] that will be presented in a random order for 7 minutes each:

- 1) slower OF: 0.5 times the individual's comfortable speed,
- 2) matched OF: same as the individual's comfortable speed,
- 3) faster OF: 2 times the individual's comfortable speed.

In order to normalize the registered EMG signals, the maximum voluntary isometric contraction (MVIC) test will be used. Each subject carries out the MVIC test 3 times for each muscle. Subjects must reach their maximum strength as quickly as possible and must keep it for 6 seconds. Subjects will perform the MVIC test in the following testing positions: prone with the knees in 30° of flexion (Mm. biceps femoris); seated with the knees in 60° of flexion, and the hips in 90° of flexion (Mm. rectus femoris). The average of the three tests will be taken for each muscle.

Example of a possible VR enhanced RAGT session

Preparation and installation subject + determining settings of the Lokomat	Getting used to the VR	Walking with slower OF	Walking with matched OF	Walking with faster OF	Uninstalling subject
20 min	1 min	7 min	7 min	7 min	3 min
Total time: 45 min					

↓
 Pause the Lokomat to put on the HMD

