2.7 Outcome

2.7.1 Biomechanical quantification of active participation

The active participation during RAGT will be measured with the use of electromyography, the force sensors and the position sensors of the Lokomat.

- **Electromyography:** with the use of surface electrodes, muscle activity of the Mm. rectus femoris and Mm. biceps femoris of both legs will be measured. Surface electromyograms of these muscles will be analyzed with the use of the 'mean absolute value' variable. It represents the area under the EMG signal (AUC) once it has been rectified, meaning that all of the negative voltage values have been made positive. The mean absolute value will be measured per minute to compare the amount of muscle activity in time within one OF speed, between different OF speeds and between the 2 VEs.

- **Force sensors:** with the use of the force sensors of the Lokomat, interaction torques between the participant and the orthosis will be measured of the 4 joints (bilateral hip and knee). These interaction torques will be used to quantify how much the participant contributes to the walking movement him or herself. The average of these interaction torques will be calculated per minute to compare the amount of force in time within one OF speed, between different OF speeds and between the 2 VEs.
- **Position sensors:** with the use of the position sensors of the Lokomat, it is possible to measure the range of motion (°) of the 4 joints (bilateral hip and knee).

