2.8 Statistical analysis

Statistics will be performed using SPSS (IBM, Chicago, IL). The significance level will be set on 5%. Descriptive statistics will be calculated for baseline participant characteristics. Means and standard deviations will be calculated for continues variables and frequencies and percentages for categorical variables. Active participation will be measured continuously during the session. Data analysis of the average of every minute will be conducted. To investigate the effect of time, the different OF speeds, and the different VEs, repeated-measures ANOVA (within-between subject design) will be done.

3. Funding

The author disclosed receipt of the following financial support for the research, authorship and/or publication of this study: fellowship of the Vrije Universiteit Brussel for one year.

4. References

- [1] I. Schwartz and Z. Meiner, "Robotic-assisted gait training in neurological patients: who may benefit?," (in eng), *Ann Biomed Eng*, vol. 43, no. 5, pp. 1260-9, May 2015.
- [2] H. K. Kang, Y. Kim, Y. Chung, and S. Hwang, "Effects of treadmill training with optic flow on balance and gait in individuals following stroke: randomized controlled trials," *Clinical Rehabilitation*, vol. 26, no. 3, pp. 246-255, Mar 2012.
- [3] O. Stoller, M. Waser, L. Stammler, and C. Schuster, "Evaluation of robot-assisted gait training using integrated biofeedback in neurologic disorders," (in eng), *Gait Posture*, vol. 35, no. 4, pp. 595-600, Apr 2012.
- [4] E. Swinnen, D. Beckwee, D. Pinte, R. Meeusen, J. P. Baeyens, and E. Kerckhofs, "Treadmill training in multiple sclerosis: can body weight support or robot assistance provide added value? A systematic review," (in eng), *Mult Scler Int*, vol. 2012, p. 240274, 2012.
- [5] I. Schwartz *et al.*, "Robot-assisted gait training in multiple sclerosis patients: a randomized trial," (in eng), *Mult Scler*, vol. 18, no. 6, pp. 881-90, Jun 2012.
- [6] K. Y. Nam, H. J. Kim, B. S. Kwon, J. W. Park, H. J. Lee, and A. Yoo, "Robot-assisted gait training (Lokomat) improves walking function and activity in people with spinal cord injury: a systematic review," (in eng), *J Neuroeng Rehabil*, vol. 14, no. 1, p. 24, Mar 23 2017.
- [7] A. Lamontagne, J. Fung, B. J. McFadyen, and J. Faubert, "Modulation of walking speed by changing optic flow in persons with stroke," *Journal of Neuroengineering and Rehabilitation*, vol. 4, Jun 2007.

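### Cheap improvement, not an error: the plan gives the no-VR Lokomat walk no role in the comparison of the two virtual environments, where a recorded pre-exposure minute could serve as a covariate

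*Combined protocol and SAP*

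**What the plan says.** The second aim (section 1.2) is the effect of the two virtual environments on active participation. Participants are randomised 1:1 to an environment (section 2.5), with 14 completers per group (section 2.2.1).

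In section 2.4 the order of events is: electrodes on; Lokomat walking without VR ("At the start of the session, participants will be habituated to walking in the Lokomat without the virtual reality"), during which the settings are determined; Lokomat stopped; headset on; one minute of VR familiarisation; then the three optic flow (OF) conditions. The same section limits some differences between people: "In order to normalize the registered EMG signals, the maximum voluntary isometric contraction (MVIC) test will be used", and "Guidance force (GF) will be set on 80% for all participants". Body-weight support and walking speed are also the same for everyone.

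Section 2.7.1 has EMG averaged per minute "to compare the amount of muscle activity in time within one OF speed, between different OF speeds and between the 2 VEs", and treats the interaction torques in the same way. Section 2.8 says "Active participation will be measured continuously during the session" and gives the model: "To investigate the effect of time, the different OF speeds, and the different VEs, repeated-measures ANOVA (within-between subject design) will be done". No covariate is named. Section 2.8 mentions baseline only for descriptive participant characteristics. The no-VR walk is not used in any comparison.

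**The concern.** OF speed is compared within participants, so stable differences between people cancel. The VE effect is a contrast between people, and its precision depends on how much participants differ in how actively they walk in the device. MVIC normalisation and common settings reduce that spread; the documents do not say how much remains.

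A measurement of the same outcomes, on the same instruments, before the assigned environment is seen would remove the part of the spread that it predicts. It would also show, and adjust for, chance imbalance between two groups of 14. The protocol has a walk at the right point in the session for this but does not use it. What is at stake is precision for aim 2, not validity. The choice has to be made in advance, because adjustment chosen after seeing the results would carry little weight.

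**Working it through.** **Inputs from the documents (section 2.2.1):** f = 0.25, alpha = 0.05, power 0.80, 2 groups, m = 3 conditions, N = 28.

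**Assumptions (not stated in the documents):** correlation rho = 0.5 between conditions; sphericity (epsilon = 1); f = 0.25 applied to the VE main effect, although section 2.2.1 gives it for the within-between calculation; R, the correlation of the baseline minute with the participant's three-condition mean, unknown and varied.

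**Step 1: reproduce the plan's N.** Within-between interaction, noncentral F with lambda = f²·N·m/(1 − rho) on 2 and 2(N − 2) df. At N = 28, lambda = 0.0625 × 28 × 3/0.5 = 10.5 on 2 and 52 df, power 0.812. Power is 0.795 at N = 27 and 0.778 at N = 26. So rho = 0.5 with sphericity reproduces 28. Other pairs do too: with epsilon = 0.8, rho of about 0.57 to 0.59 also gives 28 as the smallest even N.

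**Step 2: VE main effect, unadjusted.** In single-condition SD units, the variance of a three-condition mean is v = (1 + 2·rho)/3 = 0.667. Then lambda = N·f²/v = 28 × 0.0625/0.667 = 2.625 on 1 and 26 df, power 0.345.

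**Step 3: VE main effect, adjusted.** ANCOVA on the participant mean multiplies the residual variance by (1 − R²) and costs one df. Chance baseline imbalance costs a further factor of about 1 − 1/25 = 0.96. So lambda = 2.625 × 0.96/(1 − R²) on 1 and 25 df.

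| R | lambda | VE power |
|---|---|---|
| unadjusted | 2.625 | 0.345 |
| 0 | 2.520 | 0.333 |
| 0.2 | 2.625 | 0.344 |
| 0.3 | 2.769 | 0.360 |
| 0.4 | 3.000 | 0.384 |
| 0.5 | 3.360 | 0.422 |
| 0.61 | 4.032 | 0.488 |

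The last row takes a baseline minute that correlates with each condition as strongly as the conditions do with one another: R = 0.5/√0.667 = 0.61. Break-even R is 0.207 (0.200 if power is averaged exactly over imbalance). Simulation with 400,000 trials per value gave 0.334, 0.360 and 0.423 at R = 0, 0.3 and 0.5.

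**Step 4: precision.** The 95% interval half-width for the VE difference, in single-condition SD units, is 0.634 unadjusted and 0.649, 0.619 and 0.562 at R = 0, 0.3 and 0.5.

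**Step 5: sensitivity to rho.**

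| rho | unadjusted | R = 0 | R = 0.3 | R = 0.5 |
|---|---|---|---|---|
| 0.3 | 0.415 | 0.400 | 0.432 | 0.504 |
| 0.7 | 0.297 | 0.286 | 0.309 | 0.363 |
| 0.8 | 0.278 | 0.268 | 0.289 | 0.340 |

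R and rho are linked in practice, so this grid does not bound the gain. If the baseline behaved like a fourth condition, R would be 0.41 at rho = 0.3 and 0.86 at rho = 0.8. At rho = 0.8, lambda would be 28 × 0.0625 × 0.96/(0.867 × (1 − 0.859²)) = 7.41 and power 0.74.

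**Step 6: distance from 80%.** At rho = 0.5, N = 28 reaches 80% power only with R of about 0.84. Unadjusted, 86 participants would be needed.

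**The case against.** The strongest reply is that nothing is broken. A randomised comparison without a covariate is valid, R appears nowhere in the documents, and below about 0.21 the adjustment loses power. At R = 0.3 the gain is only 1.5 points (0.360 − 0.345). All of this stands, and it is why the point is an improvement and not an error. The power values illustrate a range of assumptions and do not predict a gain. The value of rho is a planning input inferred from N, not evidence of the real correlation.

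It is also fair that the walk is not a ready-made baseline. Section 2.4 describes habituation while settings are being found, and the Lokomat is stopped once they are defined. A reader might infer from "Active participation will be measured continuously during the session" that usable baseline data are already collected and then discarded. The text does not support that: it never says that this walk is recorded, and no steady period at final settings is described. The remedy therefore changes the procedure as well as the analysis.

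Finally, a covariate raises the question of which model tests the VE-by-OF interaction, the type of effect for which the sample size calculation reproduces. The fix has to answer that.

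What remains is the trade-off. The loss is about one point if the baseline is useless. The gain is 7.7 points at R = 0.5 (0.422 − 0.345). A view of baseline balance between the groups is gained whatever R turns out to be.

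**Conclusion.** A worthwhile, low-cost improvement to a valid analysis. With f = 0.25 for the VE main effect, rho = 0.5 and sphericity, adjustment moves VE power from about 0.34 to about 0.33, 0.36 or 0.42 at R = 0, 0.3 or 0.5, and to about 0.49 at R = 0.61. The direction of the change depends on whether R exceeds about 0.21, which the documents cannot settle.

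Two stronger readings are not supported. A reader might infer that the unadjusted VE comparison is biased; allocation is randomised, so it is not. A reader might also infer that a baseline covariate would make aim 2 adequately powered; in every case shown, power stays below 80%. Whether the trial is large enough for aim 2 is a separate question that this change does not answer.

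**What to change.** **Section 2.4.** Record one minute of steady walking without VR (EMG, torque and range of motion) once the Lokomat settings are final and before the headset is put on. Do not use the VR familiarisation minute as baseline, because the participant is then already viewing the virtual scene.

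**Section 2.8.** Prespecify each outcome's own value in that minute, with EMG on the MVIC-normalised scale, as the covariate for the VE main effect, by ANCOVA on the participant's mean over the three conditions. Keep the planned repeated-measures ANOVA, without the covariate, for every within-subject test: OF speed, time, and their interactions with VE, including VE-by-OF. Those tests then do not depend on covariate-by-condition terms. Report baseline values by group, and the unadjusted VE result as a sensitivity analysis.

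**Cost.** About one minute of recording per participant, inside the 20-minute set-up limit or added to the 45-minute session. One degree of freedom per VE model. A separate VE model per outcome: up to 12 if each muscle and joint is analysed on its own (4 EMG + 4 torque + 4 range of motion), fewer if the legs are averaged. About one point of VE power (0.345 to 0.333) if the baseline predicts nothing.

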2.5 Randomization

Subjects who agree to participate in this study will be equally randomized in a 1:1 ratio into 2 groups. For randomization, sealed envelopes will be prepared in advance and marked on the inside with a VE + or VE -. During the intervention, the speed of the OF (slow, matched or fast) will also be randomized. To participants, it will only be said that they will have to walk in the Lokomat with the VR for 21 minutes. They will not know that and when the OF speed will change.

2.6 Materials

Surface EMG electrodes will be used to measure the muscle activity of the Mm. rectus femoris and Mm. biceps femoris. Surface EMG data will be captured with the ME6000 EMG-system (Mega Electronics Ltd) using Conmed Cleartrace electrodes (Ag/AgCl) with an active diameter of 10mm.

The Lokomat has a biofeedback system that measures and displays participants' activity in real-time. With the use of force sensors, this biofeedback system measures the force of the Lokomat's drive motors. If the participant actively moves with the programmed gait pattern, the power required from the drives is small. The less active the participant is, the greater the drive force required to move his limbs according to the preprogrammed pattern. With this approach, two values are calculated for each driven joint; one for the swing phase, the other for the stance phase. This provides 8 biofeedback values per step cycle to characterize the degree of activity of the patient. Besides force sensors, the Lokomat also comprises position sensors. These sensors will be used to measure the range of motion (ROM) of the hip- and knee joints.

2.7 Outcome

2.7.1 Biomechanical quantification of active participation

The active participation during RAGT will be measured with the use of electromyography, the force sensors and the position sensors of the Lokomat.

- **Electromyography:** with the use of surface electrodes, muscle activity of the Mm. rectus femoris and Mm. biceps femoris of both legs will be measured. Surface electromyograms of these muscles will be analyzed with the use of the 'mean absolute value' variable. It represents the area under the EMG signal (AUC) once it has been rectified, meaning that all of the negative voltage values have been made positive. The mean absolute value will be measured per minute to compare the amount of muscle activity in time within one OF speed, between different OF speeds and between the 2 VEs.

- **Force sensors:** with the use of the force sensors of the Lokomat, interaction torques between the participant and the orthosis will be measured of the 4 joints (bilateral hip and knee). These interaction torques will be used to quantify how much the participant contributes to the walking movement him or herself. The average of these interaction torques will be calculated per minute to compare the amount of force in time within one OF speed, between different OF speeds and between the 2 VEs.
- **Position sensors:** with the use of the position sensors of the Lokomat, it is possible to measure the range of motion (°) of the 4 joints (bilateral hip and knee).

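### Torque is compared between the two VE groups with no allowance for body size; a prespecified body-mass covariate would remove possible noise from the second aim at almost no cost

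*Combined protocol and SAP*

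**What the plan says.** Section 2.7.1 names three measures of active participation: EMG, interaction torque and range of motion. On torque it states "These interaction torques will be used to quantify how much the participant contributes to the walking movement him or herself". The summary is a per-minute mean: "The average of these interaction torques will be calculated per minute to compare the amount of force in time within one OF speed", and further "between different OF speeds and between the 2 VEs". The last of these is the between-person comparison that serves the second aim in 1.2.

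Section 2.6 explains what the force sensors register: "The less active the participant is, the greater the drive force required to move his limbs according to the preprogrammed pattern".

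EMG is treated differently. Section 2.4 states "In order to normalize the registered EMG signals, the maximum voluntary isometric contraction (MVIC) test will be used", using the average of three tests per muscle. No comparable step is described for torque.

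Section 2.8 analyses time, OF speed and VE by repeated-measures ANOVA and names no covariate. Section 2.5 randomises 1:1 to VE and describes no stratification. Section 2.2.2 limits size only from above, at "a maximal body weight of 135 kg" and a height of 200 cm.

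**The concern.** The force needed to move a limb along a fixed path depends on the limb's mass and length as well as on the person's own effort. If that holds for the Lokomat torques, two people who participate equally but differ in size will give different readings. Within a person this largely cancels. Between the two VE groups it does not.

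At stake is the torque result for the second aim. Variation in body size would widen the between-person spread, and a chance difference in weight between two groups of 14 could be read as a difference in participation. There is also an analytic freedom: with nothing prespecified, raw or size-adjusted torque could be chosen after the results are seen.

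**Working it through.** **1. The plan's own figure.** Section 2.2.1 gives f = 0.25, alpha 0.05, power 0.80, 2 groups and 3 conditions, N = 28. Assumed, because not stated: correlation 0.5 between conditions, and sphericity. For the within-between interaction, lambda = f² × N × m / (1 − rho) = 0.0625 × 28 × 3 / 0.5 = 10.5 on 2 and 52 df. Power is 81.2% at N = 28 and 77.8% at N = 26, so 28 reproduces.

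**2. The VE main effect at the same N.** lambda = f² × N × m / (1 + (m − 1) × rho) = 0.0625 × 28 × 3 / 2 = 2.625 on 1 and 26 df, which gives power of 34.5%. On person means, d = √(4 × 2.625 / 28) = 0.61. The difference detectable with 80% power is 1.10 SD.

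**3. Chance imbalance.** The difference in mean body mass between two groups of 14 has an SD of √(2/14) = 0.38 body-mass SDs.

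**4. Model for the loss.** Torque = participation × (mass / mean mass)^b. Assumed: participation CV 30%; body-mass CV 12, 16 or 20%; VE effect 1.1 SD of participation (power 0.80 without mass noise); b = 0, 0.5 or 1. The test is a two-sided 5% comparison of person means, 14 per group, 20,000 replicates per cell. The model's sign is arbitrary. By 2.6, greater participation should lower drive force, so both directions were run.

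Power at mass CV 12 / 16 / 20%:

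| b | Raw torque, effect raises it | Raw torque, effect lowers it | Nm/kg, effect raises torque |
|---|---|---|---|
| 0 | 0.80 | 0.80 | 0.72 / 0.66 / 0.60 |
| 0.5 | 0.78 / 0.77 / 0.74 | up to 0.79 | 0.78 / 0.77 / 0.74 |
| 1 | about 0.72 / 0.66 / 0.60 | 0.75 / 0.72 / 0.68 | 0.80 |

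With mass as a covariate, power is about 0.77 to 0.79 for all three values of b.

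**5. Check by hand for b = 1.** In the reference group the variance ratio is (CVp² + CVm² + CVp² × CVm²) / CVp². At mass CV 16% this is (0.09 + 0.0256 + 0.0023) / 0.09 = 1.31; at 12% and 20% it is 1.17 and 1.48. In the other group the mean is 1 ± 1.1 × 0.30, that is 1.33 or 0.67. At 16% the ratio there is (0.09 + 0.0256 × (1.33² + 0.09)) / 0.09 = 1.53, or with 0.67 it is 1.15. The averages over groups are 1.42 and 1.23. The effect shrinks to 1.1 / √1.42 = 0.92 SD or 1.1 / √1.23 = 0.99 SD. For comparison, power is 0.72 at 1.0 SD and 0.53 at 0.8 SD, so both directions agree with the table.

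**6. Gain from a covariate at the plan's f.** If body size explains a share R² of the between-person torque variance, adjusted power for the VE main effect is 34.4% (R² = 0), 37.5% (0.10), 43.6% (0.25) or 59.5% (0.50). The detectable difference falls from 1.10 SD to 1.05, 0.95 and 0.78 SD for the last three. These figures take mass as balanced between groups. The simulation in step 4 lets it differ by chance, which is why the cost at b = 0 is 1 to 2 points there and near zero here.

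**The case against.** The strongest case against has five parts.

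- **Unscaled torque is inferred from silence** in a short protocol, and torque is already in a physical unit. EMG normalisation does not by itself oblige the authors to scale torque. This stands in part, but 2.7.1 and 2.8 are where an adjustment would be stated. The appendix concerns Lokomat settings and shows no content in this copy, so nothing is drawn from it.
- **The documents do not quantify how torque depends on mass.** Section 2.6 supports the link only as a mechanical inference, and these are healthy walkers who may leave little passive limb load for the drives. This stands. The loss could be nil.
- **A reader might infer that Nm/kg should be the main measure.** The documents do not support that. Dividing by mass when torque does not depend on it loses as much power as leaving it raw when it is proportional, and the two tie at b = 0.5.
- **A reader might infer bias, or that the OF results are compromised.** Neither follows. VE is randomised, so body size is not systematically different between groups, and OF speed and time are compared within the person.
- **A reader might point to the load left after 30% support:** 0.7 × 135 = 94.5 kg against 0.7 × 60 = 42 kg for an illustrative 60 kg person. No section says that the drives carry this vertical load, so the 2.25-fold ratio is not a measure of the effect on torque and is not used here.

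It is also fair to say that a 1.1 SD effect is not in the plan. At the plan's f = 0.25 the VE main effect has only 34.5% power, of which full proportionality would take about 3 to 11 percentage points. Body size is not the main reason that this comparison is weak.

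**Conclusion.** The point holds as a modest, inexpensive improvement to one outcome under the second aim. The between-group comparison of torque has no stated allowance for body size, and body size may add noise and chance imbalance. For an effect that would otherwise have 0.80 power, the loss runs from nothing to about 20 percentage points. The upper end needs torque fully proportional to mass, a body-mass CV of 20%, participation CV of 30%, and a VE effect that raises torque. If greater participation lowers drive force, as 2.6 describes, the worst case in this range is 0.68. All of these are assumptions; the documents supply no torque SD and no mass-torque relation. The stated N of 28 is not in question here.

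**What to change.** In 2.8, add body mass, centred at its mean, as a prespecified covariate in the between-group VE comparison of interaction torque. State there that the unadjusted comparison and Nm/kg are supportive only. Centring matters because with an uncentred covariate in a repeated-measures ANOVA the within-person effects would be evaluated at a mass of zero. The OF and time tests can be kept as planned.

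State also that body mass is recorded at baseline. It must be known already to apply the 135 kg limit and to set the 30% support, so no new measurement is needed.

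Cost: a sentence or two in 2.8 and one degree of freedom, which is about 1 to 2 percentage points of power if mass turns out to be irrelevant.
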